Background: Overweight and obesity are defined as abnormal or excessive fat accumulation that may impair health, leading to reduced life expectancy and/or increased health problems¹, and results from an energy imbalance. In basic terms, *obesity* is defined as having more body fat than is considered healthy², which, in turn, is defined as a body mass index (weight (kg)/height (m)²) of 30.0 or higher³. Currently in the United States, about 38% of the American adult population is considered obese³⁻⁷, which translates to one in three Americans being obese.

Low level laser therapy (LLLT) is a new novel non-invasive procedure that removes excess fat without the negative side effects associated with surgical methods. LLLT also has the potential to enhance motivation for weight management as LLLT treatment can provide immediate feedback to the patient or study participant in the form of lost inches which can be seen by the individual. LLLT has been associated with a reductions in waist circumference of 6 inches as reported in prior studies, with some noting more extensive reductions of up to 12 inches with 6 treatments.

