Clinically, the LLLT treatments can vary from 6 to 28 treatments and a frequency of 1-3 times per week depending on the patients' preference and ability to pay. Our research team conducted a previous feasibility study of 45 overweight/obese subjects looking at the use of 12 LLLT treatments over the course of 12 weeks (one treatment per week) with the end goal of reducing central adiposity. In this prior study (IRB 14-002370), subjects were randomized to 1 of 3 conditions (LLLT, lorcaserin, and LLLT + lorcaserin). This study demonstrated feasibility by recruiting the goal of 45 obese subjects within 3 months. The subjects assigned to LLLT did not have any adverse events reported during the 6 months of the trial and although the sample size was too small for any significant findings, the LLLT did show a reduction in body circumference (2.3 to 4.0 cm reduction) and a reduction in weight (1 to 3.5 kg reduction). This 2014 study was followed by another study (IRB 16-004817) in which our study team compared different frequencies of administering 12 LLLT. The compared frequencies were 12 treatments administered once per week, twice per week or 3 times per week. This latter study found that 12 treatments delivered twice per week (for up to 6 weeks) was the most optimal⁸ frequency when considering maintenance of the weight loss post treatment. Although weight loss and inches lost were significant with LLLT, a theory does exist that when LLLT is accompanied by lifestyle modification, including a reduction in dietary intake as well as an increase in caloric expenditure through moderate-intensity activity, the impact of the weight and inches lost will be greater. The overarching goal of this study is to test this hypothesis.

For the purposes of this study, we will define overweight as having a body mass index [BMI] of 25-29.9 kg/m² and obesity as a BMI of 30-39.9 kg/m². In this pilot study we will randomize 60 overweight and obese individuals to one of two treatment arms:

- LLLT + Lifestyle Modifications and Wellness Coaching (GROUP 1),
- Sham LLLT + Lifestyle Modifications and Wellness Coaching (GROUP 2).

Study Design and Methods

Methods:

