Study Design: This will be a randomized clinical trial. We will obtain preliminary data on the efficacy of LLLT as an adjunct to Lifestyle Modification and Wellness Coaching. We will focus this study on 60 overweight and obese adults with a BMI of 25 to 39.9. We will assess changes in weight, waist circumference, A1C and CRP at end of LLLT treatment (week 6) and end of Lifestyle Modification/Wellness Coaching intervention (week 12). Participants will be randomized to one of the following groups:

- LLLT biweekly for 6 weeks + Lifestyle Modification and Wellness Coaching (GROUP 1),
- Sham LLLT biweekly for 6 weeks + Lifestyle Modification and Wellness Coaching (GROUP 2).

Study Procedures: We will use standardized procedures to ensure that uniform instructions are provided to all participants and that recruitment and screening result in the enrollment of appropriate study participants. All Study Case Report Forms will be administered online using REDCap and will also function as study source documents. Study participant data on this system will be identified using unique subject IDs, not personal identifiers. This data entry system will provide immediate feedback on data integrity issues, including implausible entries, and checks of consistency between variables.

Study Process

Study Visit:

- Each visit will have a window from midpoint of prior visit to midpoint of latter visit.
- If a subject cannot reschedule their visit within the study visit window, that visit is categorized as “missed”.
- A subject is allowed 3 consecutive missed visits before “drop” procedure is commenced.

Post Baseline, *data collection options* for all self-assessments (i.e. surveys and questionnaires):

- E-mailed via REDCap program one week prior to the visit. Subject will be asked to complete and submit back to the site prior to the visit.
- In person/on paper at the clinic visit, if the email data was not received by the site prior to the visit.

Screening Phase		Treatment Phase							Post Treatment Follow-up		
Pre-screen	Consent/Screen/ Baseline	0	1	2	3	4	5	6	7	S	8
Visit No.		0	1	2	3	4	5	6	7	S	8
Visit Type	P	C	C	C	C	C	C	C	C	P	C
Visit Week	-2	0	1	2	3	4	5	6	7		12
Allowable window (in days)			± 14	± 2	± 3		± 14				
Study Entry/Screening											
Informed Consent		X									
Inclusion/Exclusion	X	X									
Demographics/Weight Loss History		X									
Safety											
Adverse Events (5) & Concomitant Medications (6)		X	X	X	X	X	X	X		X	

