- Lifestyle Modifications: At Baseline, the study assistants will complete an additional brief (10-minute) individual behavioral intervention. Introduce and review the key tenets of lifestyle modification utilizing the “My Weight Solution®” manual and motivate the patient toward a steps goal using Wellness Coaching Approaches. Topics to be covered will include: motivational strategies, social support, goal setting strategies, nutritional recommendations and strategies for physical activity. A copy of “My Weight Solution®” will be given to the study participant to keep and to be used by the study participant at their convenience. The book chapters include: Introduction [Not just another diet, Getting started, Are you Ready]; Part 1: Lose It! [Add 5 Habits, Break 5 Habits, Adopt 5 Bonus Habits], Part 2: Live It! [Your Live It! Strategies, Strategy 1: Set Realistic Goals, Strategy 2: Follow the pyramid, Strategy 3: Burn calories by being active], Bonus section: How to stick with your commitment [Change Behaviors, Change Your Mind, Stay Connected, Overcome Challenges].
- Wellness Coaching: Study Staff, who are trained as Wellness Coaches (SF and SL) will introduce the patient to Lifestyle Modification approaches, and review and discuss the different chapters of the book “My Weight Solution®”, at the baseline visit. Lifestyle modification will consist of caloric reduction of 500 -750 calories from current needs depending on BMI. Additionally, subjects will be advised to target 150 minutes of moderate intensity activity with the type of activity varying by patient's current degree of mobility. This visit will be approximately 20-30 minutes in duration. During each week the Wellness Coaches will meet with the participants for a short education session on another aspect of the lifestyle modifications utilizing “My Weight Solution®”. Each of these follow up sessions can last anywhere from 10-15 minutes. During the first 6 weeks of study participation (during the LLLT/Sham LLLT treatments) the sessions will be individualized and in person.
- LLLT: In this trial, subjects randomized to receive LLLT or sham LLLT with Lifestyle Modification/Wellness Coaching will undergo 12 treatments – twice per week for 6 weeks.

[figure not shown]

Figure 2. LLLT device - Emerald® by Erchonia

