The study team will register the subject in the redcap database and once registered, the randomization program within the redcap patient record will identify the subject as being enrolled in Group 1 (LLLT) or Group 2 (Sham LLLT). The study team will then flip a switch on the LLLT machine to A or B depending on the group assigned and then follow the procedure administration protocol for the LLLT for each session (note, the same process is followed regardless of the group assigned to patient – after the switch is placed in the correct setting):

- The study participant is correctly fitted with the safety glasses (see manual for specifics of the safety glasses).
- The participant lies comfortably flat on his or her back on the procedure table such that the front area of the subject’s body is facing upwards.

- The Erchonia® Emerald 10 Headed Scanner diodes are positioned within 6 inches above the subject's lower and upper abdomen, stomach, centered along the body's midline (the "line" that vertically "dissects" the body into two equal halves).
- The Erchonia® Emerald 10 Headed Scanner is then activated for 15 minutes over the subject's **anterior** (frontal) region. Each scanner emits to the subject a laser beam of approximately 16 mW ± 2mW with a wavelength of 532 nm, and creates a spiraling circle pattern that is totally random and independent from the others. These patterns overlap each other to guarantee total coverage within the target area of approximately 80 in²/516 cm².
- The participant then turns over to lie flat on his or her stomach such that the posterior treatment area of the subject's body encompassing the region spanning from the participant's back down though the central body region is facing upwards.
- The Erchonia® Emerald 10 Headed Scanner diodes are positioned at a distance of approximately 6 inches above the posterior treatment area, centered along the body's midline, the same as for the anterior region.
- The Erchonia® Emerald 10 Headed Scanner is then activated for 15 minutes over the subject's **posterior** (back) region. Each scanner emits to the subject a laser beam of approximately 16 mW ± 2mW with a wavelength of 532 nm, and creates a spiraling circle pattern that is totally random and independent from the others. These patterns overlap each other to guarantee total coverage within the target area of approximately 80 in²/516 cm².
- The participant's safety glasses are removed and the procedure administration session is over.

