Based upon our recruitment data from recent weight loss studies and a wait list of participants who are interested in this treatment, we estimate recruiting on average 3-4 study participants per week. Those who meet study criteria will be invited to participate in this study. In this study, all 60 study participants will receive some form of treatment and be in the study for 3 months. The following is a listing of interventions each participant will receive and the LLLT/sham LLLT aspect is based on the randomization group assigned:

1. 12 individual treatments of LLLT or sham LLLT (twice per week for 30 min each), while also utilizing Lifestyle Modification/Wellness Coaching.
2. Weekly sessions Lifestyle Modification discussion during the 6 weeks of individual treatments.
3. Three Goal setting discussions with Mayo Trained Wellness coaches during 6 weeks of treatments.

Inclusion Criteria: Potentially eligible subjects must:

1. be 18 years of age or older.
2. have a BMI 25–39.9 kg/m².
3. be able to participate fully in all aspects of the study; and
4. have understood and signed study informed consent.

Exclusion Criteria: Subjects will be excluded if they:

1. have used weight loss medications or participated in a weight loss program within the past 30 days.
2. are currently taking medications or supplements known to affect weight, such as insulin or sulfonylurea, prednisone or *garcinia cambogia*.
3. have had weight fluctuations of 5 pounds or more in the past month.
4. have an implanted device (including pacemaker or lap band) in the targeted area of LLLT.
5. have a known active eating disorder.
6. have a known, active, untreated clinically significant psychiatric condition (alcohol or substance abuse, psychosis, bipolar disorder, or depression).
7. have used an investigational drug within 30 days of study enrollment.
8. Reports being currently pregnant, lactating, or are of child-bearing potential or are likely to become pregnant during the LLLT treatment phase and are unwilling to use a reliable form of contraception. Acceptable forms include:
 - a. Hormonal methods, such as birth control pills, patches, injections, vaginal ring, or implants
 - b. Barrier methods (such as a condom or diaphragm) used with a spermicide (a foam, cream, or gel that kills sperm)
 - c. Intrauterine device (IUD)

- d. Total hysterectomy or tubal ligation
- e. Abstinence (no sex)

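### The group assignment given to the study team discloses the arm before the coded A/B switch is set, and the protocol does not state who is masked

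*Combined protocol and SAP*

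**What the plan says.** The LLLT part of the Intervention section in the combined protocol and SAP sets out the sequence. Once the subject is registered, "the randomization program within the redcap patient record will identify the subject as being enrolled in Group 1 (LLLT) or Group 2 (Sham LLLT". Next, "The study team will then flip a switch on the LLLT machine to A or B depending on the group assigned". A note in the same sentence adds that "the same process is followed regardless of the group assigned to patient" once the switch is in position.

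The list of arms at the end of Background gives the key to the group numbers, for example "Sham LLLT + Lifestyle Modifications and Wellness Coaching (GROUP 2". Study Design repeats it. Study Design calls the study a randomized clinical trial and says nothing about blinding.

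On records, Study Procedures says: "All Study Case Report Forms will be administered online using REDCap and will also function as study source documents".

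On contact during treatment, the Wellness Coaching paragraph says: "During the first 6 weeks of study participation (during the LLLT/Sham LLLT treatments) the sessions will be individualized and in person". Subject population also lists "Three Goal setting discussions with Mayo Trained Wellness coaches during 6 weeks of treatments".

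**The concern.** A sham arm is there to separate the effect of the laser from the effects of attention, expectation and effort. A two-position coded switch is a sensible way to protect that separation, because an operator can deliver the assigned treatment without knowing which it is. Here the assignment reaches the study team by group before the switch is touched, so the code does not protect the person using it.

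Two routes to bias follow, and they differ in strength:

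- **Waist circumference (secondary aim)** is read by hand with a tape. An assessor who knew the arm could influence the reading directly.
- **Fat mass (primary endpoint)** is read by the InBody device. Knowledge of the arm could act only indirectly, through unequal coaching or through staff conveying the arm to participants, whose diet, activity or motivation might then change.

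The protocol gives a reason to take the second route seriously. Background says that "LLLT also has the potential to enhance motivation for weight management", and motivation is scored weekly as an outcome.

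**Working it through.** This is mainly a reading of the text, so the relevant places are set side by side.

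1. **Order of events.** Registration comes first, then identification of the group by REDCap, then the switch. The study team needs the assignment in order to choose A or B.

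2. **Does the group number reveal the arm?** Yes. The arm names in brackets might be an explanation for the protocol reader and not the literal screen text. That does not restore masking: Background and Study Design both equate Group 1 with active and Group 2 with sham, and the team must also know which group corresponds to which switch position.

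3. **Is masking stated elsewhere?** No sentence in the available text says that participants, laser operators, coaches or waist assessors are kept unaware of the arm. The note on identical steps standardises the session. It could help conceal the arm from the participant, but not from a person who has just read the assignment. The text does not say whether sham output looks like the active 532 nm beam.

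4. **Who else could see the allocation?** It is held in the REDCap patient record, and the case report forms are also in REDCap. No access limit is given. Staff are described collectively, with no separation of roles. By the initials given, one of the two coaches is also the study lead who directs the coordinators. This does not show that a coach or waist assessor sees the allocation, or that one person both operates the laser and measures the waist.

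5. **Contact during the treatment period.** Laser or sham sessions: 2 per week × 6 weeks = 12. Weekly coaching follow-up: 6 × 10 = 60 minutes to 6 × 15 = 90 minutes. The text does not say whether the three goal-setting discussions are additional.

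6. **Can the bias be sized?** The plan's own power figure reproduces. Inputs from Sample-size Justification are SD 1.6 kg, 30 per group, difference 1.1 kg and two-sided alpha 0.05.
   - SE of the difference = 1.6 × √(2/30) = 0.413 kg.
   - Normal approximation: 1.1/0.413 − 1.960 = 0.70, giving 75.9% power. The two-sample t calculation (58 df) gives 74.5%. The plan states 75%.
   - With no laser effect, assumed spurious shifts of 0.2, 0.3 and 0.4 kg give rejection rates of 7.6%, 11.0% and 15.9% (noncentral t, noncentrality = shift/0.413, critical value 2.002).

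   Those rates depend entirely on the assumed shift, and the documents give no basis for choosing one. They also concern the machine-read endpoint, where the route is only indirect. For waist, the more exposed endpoint, the documents give no SD for this regimen. The rates are therefore not part of the finding.

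**The case against.** The strongest reply has four parts.

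- **Scope.** A reader might infer that the plan unmasks the staff as a whole. The documents do not support that. They show only that whoever randomizes and sets the switch can know the arm. Exposure of coaches and waist assessors is a possibility left open by silence on access and roles.

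- **Participants.** A reader might also infer that participants learn their arm. That is not supported either. A sham, a coded switch, safety glasses fitted under the common procedure and identical steps could all conceal the arm from them. The fair statement is that participant masking is not stated.

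- **Existing safeguards.** Study Procedures promises standard procedures and the same instructions for everyone. The schedule's footnotes hold visit times to within 2 hours. The waist method fixes the anatomical level, tape tension and phase of breathing. Both arms use one coaching manual. Intake, steps and attendance are logged, and the Data Analysis Plan presents compliance by group, so some unequal effort could be detected. These measures narrow both routes, and this part of the reply stands. None of them is masking.

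- **Unseen material.** Consent pages were removed from the text reviewed, and the IRBe application and the device manual are cited but not supplied. Any of these might describe masking. That limits what can be said about absence. It does not change the LLLT procedure, which would then need to be made consistent with them.

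**Conclusion.** The point holds in a limited form. As written, the LLLT procedure discloses the arm to whoever randomizes and sets the switch, which defeats the coded switch. This is a stated procedure and not merely missing detail, and confidence in it is high. Alongside it, masking by role, access to the allocation field and separation of roles are not stated in the available text. Confidence in that part is lower because of the material not seen.

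The threat is direct for waist and indirect for fat mass. Its direction and size are unknown. A reader might take the illustrative rejection rates as a measure of bias, but they rest on assumed shifts and should carry no weight. The trial can still serve its stated purpose of providing preliminary evidence. This is a cheap improvement that should be made, and not a reason to set the comparison aside.

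**What to change.** In the LLLT procedure:

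- Replace the group identification with wording such as: *REDCap returns switch position A or B only, without group number or arm name, in a field visible only to laser operators.* Have the switch set from that field.
- Add: *The A/B key is held until database lock by a person outside the clinic team, with an emergency unblinding route. Participants, laser operators, wellness coaches and waist assessors have no access to the key.*
- State whether active and sham output look alike to operator and participant. If they do not, keep the allocation field hidden from coaches and waist assessors where existing staffing allows, and report any remaining unmasking as a limitation. The documents do not show that the team is large enough for full separation of roles.
- If participants were already treated under the current text, report possible staff unblinding as a limitation.

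The cost is a REDCap label and access change and a few protocol sentences. There are two downsides. A key holder must be found, who is also reachable for emergency unblinding. And a key with only two codes can unmask everyone once one participant's arm is known.
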